5.6. Duration of Follow Up

Version Date: April 18, 2023

Participants will be followed for 6 months (24 weeks) after removal from protocol therapy or until death, whichever occurs first. Participants removed from protocol therapy for unacceptable adverse event(s) will be followed until resolution or stabilization of the adverse event.

5.7. Criteria for Taking a Participant Off Study

Participants will be removed from study when any of the following criteria apply:

- Lost to follow-up
- Withdrawal of consent for data submission
- Death
- Investigators discretion

The reason for taking a participant off study, and the date the participant was removed, must be documented in the case report form (CRF). In addition, the study team will ensure the participant's status is updated in OnCore in accordance with REGIST-OP-1.

6. DOSING DELAYS/DOSE MODIFICATIONS

There will be no modifications to the dose of psilocybin given to study participants.

Modifications of the number, length, content and day of preparation and integration sessions will be allowed after the first few patients, as finding the most feasible, safe and effective dose of psychotherapeutic support and refining the treatment manual are major objectives of this study. Decisions to modify the psychotherapeutic protocol will be made by the PI and the study psychiatrist. Changes and reasons for changes will be documented.

7. ADVERSE EVENTS: LIST AND REPORTING REQUIREMENTS

Adverse event (AE) monitoring and reporting is a routine part of every clinical trial. The following list of reported and/or potential AEs (Section 7.1) and the characteristics of an observed AE (Section 7.2) will determine whether the event requires expedited reporting in addition to routine reporting. Because this study is being completed in patients with terminal illness, medical events or deaths due to the primary diagnosis (e.g. cancer) are expected.

The research team will not require expedited reporting to the DF/HCC IRB for primary diagnosis-related medical events or deaths (see section 7.4.4 below).

The principal investigator will be responsible for monitoring and reporting all adverse events to the DFCI IRB for this study, but in the event that the principal investigator is unavailable, the coinvestigators will assume this responsibility. The role of the responsible person is to 1) identify the concern, 2) develop the appropriate response to the concern with the use of consultants if necessary and 3) ensure proper reporting of concerns to the IRB.

All potential adverse events will be reported to the PI. The PI in consultation with Co-investigators will classify events according to level of severity. Details will be recorded on an adverse case report form as well as logged on a secure spreadsheet for reporting to the IRB.

The adverse event case report form will include a description of all undesirable experiences, required interventions, and an assessment of the subject after the event if possible. An estimate of the extent of injury, and prevention strategies will be reported. The principal investigator will classify the relationship of the study protocol to the event as follows:

- Unrelated: The event is clearly related to factors such as the subject's clinical state, not with the study protocol.
- Unlikely: The event was most likely related to factors such as the subject's clinical state, not with the study protocol.
- Possible: The event follows a reasonable temporal sequence associated with participating in the study and/or is consistent with events related to responding to queries about stress/drug craving but is possibly related to factors such as the subject's clinical state.
- Probable: The event follows a reasonable temporal sequence associated with participating in the study and/or is consistent with events related to dosing of psilocybin in the study and cannot be reasonably explained by factors such as the subject's clinical state.
- Definite: The adverse event is clearly related to the investigational agent/procedure i.e. an event that follows a reasonable temporal sequence from administration of the study intervention, follows a known or expected response pattern to the suspected intervention, that is confirmed by improvement on stopping and reappearance of the event on repeated exposure and that could not be reasonably explained by the known characteristics of the subject's clinical state.

The severity of an adverse event in both groups is defined as a qualitative assessment of the degree or intensity of an adverse event as determined by the principal investigator following CTCAE Version 5.0 severity ratings:

- Grade 1 Mild; asymptomatic or mild symptoms; clinical or diagnostic observations only; intervention not indicated.
- Grade 2 Moderate; minimal, local or noninvasive intervention indicated; limiting ageappropriate instrumental Activities of Daily Living (ADL).
- Grade 3 Severe or medically significant but not immediately life-threatening; hospitalization or prolongation of hospitalization indicated; disabling; limiting self-care ADL.
- Grade 4 Life-threatening consequences; urgent intervention indicated.
- Grade 5 Death related to AE.

A Semi-colon indicates 'or' within the description of the grade. A single dash (-) indicates a

Grade is not available. Not all Grades are appropriate for all AEs. Therefore, some AEs are listed with fewer than five options for Grade selection.

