5. TREATMENT PLAN

5.1. Treatment Regimen

Version Date: April 18, 2023

[figure not shown]
The treatment regimen consists of a single administration of psilocybin 25 mg orally combined with a supportive psychotherapy including 2 preparation sessions and 2 integration sessions.

The study schema is the following:

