5.3. Agent Administration

Administration – A capsule of psilocybin is administered orally with a full glass of water. Capsules should not be opened or chewed.

Dosing – This is a single dose study. Capsules contain 25 mg of pharmaceutical grade psilocybin, corresponding to the recommended dose in previous studies of healthy volunteers^{64,65} and cancer patients^{8,9,27}.

Observation period – The participant will have adequate counselling and preparation ahead of dosing, and after ingesting the dose will be attended by two therapists, for the subsequent 8 hours. The setting will minimize distraction and interruption, and the patient will be attended following the dose by the therapists trained in providing reassurance and a safe environment until the effects of the single dose have dissipated. Upon discharge from the study setting, the patient will be delivered to the care of a responsible individual who can observe the patient for the remainder of 24 hours after the dose was administered.

Protocol specific procedures –Blood pressure and heart rate will be measured at the following time-points after psilocybin administration (V3): 30, 60, 120, 180, 240, 300, and 360 min (± 10 minutes). Although there have been no reports of their use in well reported clinical trials with oral psilocybin, medications should be available for the treatment of causal symptomatic hypertension, agitation, or severe psychosis. Typically, these supplies are two dosage units of labetalol, nitroglycerin, lorazepam and/or diazepam, and risperidone or similar orally-disintegrating antipsychotic.

Oral Agents – Participants will be advised to avoid consuming high fat meals for one hour before and after study drug consumption. Examples of foods to avoid include those high in butter, cream, oil, cheese, whole milk, mayonnaise, salad dressing, jam, syrup, honey, nuts, as well as

soft drinks, juices, sweets or desserts, pastas, breads, crackers, chips and meats. No other protocol specific procedures are necessary.

Caregiver Precautions – Study participants should not drive or operate heavy machinery for 24 hours post study drug consumption.

5.4. **General Concomitant Medication and Supportive Care Guidelines**

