7.3. Adverse Event Characteristics

• CTCAE term (AE description) and grade: The descriptions and grading scales found in the revised NCI Common Terminology Criteria for Adverse Events (CTCAE) version 5.0 will be utilized for AE reporting. All appropriate treatment areas should have access to a copy of the CTCAE version 5.0. A copy of the CTCAE version 5.0 can be downloaded from the CTEP web site

http://ctep.cancer.gov/protocolDevelopment/electronic_applications/ctc.htm.

• For expedited reporting purposes only:

- AEs for the study agent that are listed above should be reported only if the adverse event varies in nature, intensity or frequency from the expected toxicity information which is provided.
- Other AEs for the protocol that do not require expedited reporting are outlined in the next section (Expedited Adverse Event Reporting) under the sub-heading of Protocol-Specific Expedited Adverse Event Reporting Exclusions.

• **Attribution** of the AE:

- Definite The AE *is clearly related* to the study treatment.
- Probable The AE *is likely related* to the study treatment.
- Possible The AE *may be related* to the study treatment.
- Unlikely The AE *is doubtfully related* to the study treatment.
- Unrelated The AE *is clearly NOT related* to the study treatment.

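### Section 7 makes recurrence on re-exposure a condition of a Definite rating, which a psilocybin event cannot meet after one dose; section 7.3 sets no such condition, so the two scales can rate one event differently

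*Combined protocol and SAP*

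**What the plan says.** Section 7 (introductory text) assigns the rating: "The principal investigator will classify the relationship of the study protocol to the event as follows". Five levels follow: Unrelated, Unlikely, Possible, Probable and Definite.

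- **Definite** covers an event that is "clearly related to the investigational agent/procedure". The definition then lists reasonable timing, a known or expected response pattern, a link "confirmed by improvement on stopping and reappearance of the event on repeated exposure", and no reasonable explanation in the participant's clinical state. These are joined as cumulative conditions.
- **Probable** covers an event with reasonable timing and/or one that "is consistent with events related to dosing of psilocybin in the study and cannot be reasonably explained by factors" of the participant's clinical state. It has no re-exposure condition.
- **Possible** offers, as an and/or alternative to reasonable timing, that the event "is consistent with events related to responding to queries about stress/drug craving".

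Section 7.3, under Attribution, lists the same five labels with one-line definitions. Definite there means that the event "is clearly related" to the study treatment, and nothing more is required.

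On exposure, section 5.1 describes "a single administration of psilocybin 25 mg orally combined with a supportive psychotherapy including 2 preparation sessions and 2 integration sessions", and section 5.3 says "This is a single dose study". Section 6 allows no change to the psilocybin dose. Section 8.10 says that a participant who vomits after swallowing the capsule is not given another.

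Section 13.2.1 lists adverse events and their relationship to the therapy among the safety outcomes.

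**The concern.** A rating rule should be one that the rater can apply in the trial at hand. Section 7 ties its highest level to what happens when a drug is stopped and given again. That suits repeated dosing. Here one capsule is given, there is no course to stop, and there is no second exposure on which an event could reappear. Acute effects that section 7.2 itself expects, such as a rise in blood pressure or nausea, could not be called Definite on that scale however plain the link.

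Section 7.3 removes the obstacle but creates a second problem: two definitions of one label, with no statement of which applies on the case report form. In a trial of 15 patients the causality results will rest on few events, so the choice of scale could visibly alter how those events are described. An absence of Definite events could also be read as reassurance when it came from the definition.

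**Working it through.** No formula applies and the plan states no figure to reproduce. The check compares what each rule requires with what the protocol allows.

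**Step 1: can the section 7 condition be met for psilocybin?**

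- Exposures needed for an event to reappear on repeated exposure: at least 2.
- Exposures per participant (sections 5.1 and 5.3): 1.
- Routes to a further exposure: none. Section 6 allows no dose modification and section 8.10 excludes a replacement capsule.

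Since 1 < 2, the condition cannot be met. Because it is joined to the other conditions by a conjunction, failing it rules out Definite.

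**Step 2: where does such an event go?** Take one that meets every Definite condition except re-exposure.

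| Condition | Definite (section 7) | Probable (section 7) | Does the event meet it? |
|---|---|---|---|
| Reasonable timing | required | sufficient for its and/or limb | yes |
| Known response pattern | required | the other and/or alternative is consistency with psilocybin dosing | yes |
| No reasonable explanation by clinical state | required | required | yes |
| Improvement on stopping, reappearance on re-exposure | required | not required | cannot be met |

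The event satisfies Probable in full. It does not fall to Possible, which is for events that the clinical state might explain. The shift is one level, from Definite to Probable.

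**Step 3: the same event on both scales.** Suppose blood pressure rises within an hour of the capsule, with no other explanation. Section 7 gives Probable at most. Section 7.3 permits Definite if the rater judges the link clear.

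**Step 4: what depends on the difference?**

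- Events rated Possible or higher: no change, because Probable and Definite both lie in that group.
- Reporting times (section 7.4.3): Possible, Probable and Definite share one row and one set of deadlines. The row for Unrelated and Unlikely shows the same times.
- Reporting exclusions (section 7.4.4): sorted only as related or unrelated.
- Safety hypothesis (section 1.3): refers to serious events related to the intervention and names no levels.
- Causality results (section 13.2.1): the split between Definite and Probable is affected.

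**Step 5: the drug-craving phrase.** It is one side of an and/or, so reasonable timing alone satisfies that limb of Possible. The phrase need not change a rating. Like the mention of both groups in the severity sentence of this single-arm protocol, it appears to come from another study.

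**The case against.** The strongest reply is that little follows from the defect. No deadline, exclusion, hypothesis or listed monitoring input separates Definite from Probable. The data and safety monitoring information in section 12.2 is not filtered by attribution, and the manufacturer's dataset in section 7.8 asks for relationship to study drug without naming levels. Section 13.3.2 promises only adverse event incidence, and no five-level causality table is specified. All of this stands, and it limits the size of the point.

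The two scales also share their labels, and both open Definite with the idea of a clear relationship. The demonstrated conflict is one added clause at one level. The scales also differ in what they rate (study protocol against study treatment), but the main difference is that clause.

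A reader might infer that no adverse event of any kind could be rated Definite in this trial. The documents do not support that. Section 7.3 permits the rating. Section 7's own definition covers procedures as well as the agent, and therapy sessions and assessments are repeated, so a procedure-related event could in theory recur. A reader might also infer that events would be pushed down to Possible, or that totals of related events would shrink; Steps 2 and 4 show otherwise.

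What the reply does not remove is that section 7 contains a condition that cannot be applied to the study drug, and that a second definition of the same label gives a different answer.

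**Conclusion.** The point holds in a limited form. On the section 7 scale an event attributed to psilocybin can be rated no higher than Probable. On the section 7.3 scale the same event can be Definite. The documents do not say which scale governs.

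The size is a one-level shift, Definite to Probable, for psilocybin events that would otherwise qualify as Definite. The number of such events cannot be derived from the documents. The conclusion assumes that section 7's conditions are read as cumulative, as they are written, and that no participant receives a second dose. It does not depend on a sample size, an event rate or a significance level.

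This is a fault of wording with a small effect on one reported safety outcome. It does not affect the capture of adverse events. It is worth correcting because the relationship of events to the therapy is a named outcome and the correction is cheap.

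**What to change.** 1. In section 7, delete from Definite the condition on improvement after stopping and reappearance on re-exposure. Keep the timing, response-pattern and alternative-cause criteria.
2. In section 7, remove the stress and drug-craving wording from Possible.
3. In section 7.3, replace the separate definitions with a reference to the amended section 7 scale, and state that this scale is used for all adverse event attribution.

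The opposite route, dropping section 7's definitions in favour of section 7.3, would also end the conflict. But it would discard the timing and alternative-cause criteria and leave the rater with one-line descriptions.

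The cost is a protocol wording amendment and a matching check of the case report form. Any events already rated would need the scale used to be confirmed. No new data, visits or participants are required.

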7.1. Adverse Events and Potential Risks

Version Date: April 18, 2023

Previous studies in healthy volunteers and cancer participants (advanced and non-advanced cancer) have shown oral psilocybin to be well-tolerated in a controlled setting. No drug-related serious adverse events were reported. Overall, the most commonly reported adverse events associated with psilocybin administration are psychological in nature and include transient anxiety, negative emotional states and paranoid/delusional thinking during psilocybin sessions. Sci. Such transient episodes of fear or anxiety respond well to reassurance and have not required pharmacological intervention. In previous clinical experience, acute psychological events were resolved by the end of the dosing day. Rates of prolonged psychiatric symptoms of any kind following psilocybin exposure in healthy study participants are estimated to be 0.08-0.09%.

Cardiovascular changes including increased BP and heart rate, mild and transient nausea, and mild and transient headaches are also reported with psilocybin administration.

These events are therefore examined further in this section in the population of patients with cancer who participated in recent psilocybin trials.

The Harbor-UCLA Study was a randomized, double-blind, placebo-controlled crossover design study (NCT00302744) to evaluate the efficacy of psilocybin in 12 adults (11 females) with advanced-stage cancer (various types) and reactive anxiety. ⁶⁸ The dosing sessions were spaced several weeks apart, and participants would receive either oral psilocybin (0.2 mg/kg) or oral placebo (niacin, 250 mg) in a randomized order. Assessments included monitoring for temperature, heart rate and blood pressure, and dosing sessions concluded with self-reported participant outcomes. The duration of follow-up was six months following the second dosing session.

No serious adverse events were reported during the study, and no adverse psychological effects arose from treatment. Adverse events were collected during study administration and solicited during monthly follow-up phone calls. No untoward cardiovascular sequelae was observed, though treatment with psilocybin produced transient increases in blood pressure (BP) and heart rate as compared to placebo. In response to psilocybin, mean maximum systolic BP increased from 117 ± 4.3 mm Hg to 138.9 ± 6.4 mm Hg, mean maximal diastolic BP increased 69.6 ± 2.7 mm Hg to 75.9 ± 3.4 mm Hg, and mean maximal heart rate increased from 70.4 ± 4.3 beats per minute to $81.5 \pm (5.8)$ beats per minute. No additional information on adverse event reporting was available.

The John Hopkins Study was a randomized, double-blind, crossover study (NCT00465595) to investigate the effects of psilocybin dose (low vs high dose) on a variety of outcome measures relevant to anxiety or depressive disorders exacerbated by cancer diagnosis.⁸ Participants were initially randomized to either the low dose oral psilocybin (0.014 mg/kg or 0.042 mg/kg), meant to act as placebo, or high dose oral psilocybin (0.31 mg/kg or 0.43 mg/kg), followed by crossover approximately five weeks later. The low dose was permanently

adjusted to 0.014 mg/kg due to concern that a 0.042 mg/kg dose might not serve effectively as an inactive placebo, and the high dose was similarly adjusted from 0.43 mg/kg to 0.31 mg/kg after two of the first three participants to receive the 0.43 mg/kg dose were discontinued from the study. Monitoring for adverse events occurred during dosing days up to six hours post-dose, and participant reported outcomes were solicited for up to six months following the second

No serious adverse events were attributed to psilocybin. The most frequent adverse events occurring during psilocybin dosing sessions (both low dose and high dose) are shown in Table 7.1-1. With the exception of headache, all adverse events had resolved fully by the end of the sessions. The most frequent adverse events were transient moderate increases in systolic and/or diastolic blood pressure (DBP) after psilocybin, psychological discomfort, anxiety, and physical discomfort. Episodes of elevated systolic blood pressure (>160 mm Hg) occurred in 18 of 53 (34%) high dose sessions, as compared to 17% (N = 9) of the low dose "placebo" sessions. Episodes of elevated diastolic blood pressure (>100 mm Hg) occurred in 7 of 53 (13%) high dose sessions, and 1 of 52 (2%) of the low dose sessions. One participant experienced a transient peak blood pressure (214/114 mm Hg) during the high dose session that met severity criteria, but not the duration (15 minutes) criteria for pharmacologic intervention, and therefore no intervention was delivered.

Psychological discomfort was reported in 17 of 53 (32%) of high dose sessions and 6 of 52 (12%) low dose sessions. Anxiety was reported in 14 of 53 (20%) of high dose sessions, and 8 of 52 (15%) low dose sessions. Episodes of physical discomfort (any type) occurred in 21% of high dose sessions and 8% of low dose sessions.

One instance of mild headache was reported during a high dose session. Toward the end of this study, the study team became interested in documenting the occurrence of delayed headache after psilocybin sessions. Of the 11 (of 53) participants queried, two (18%) reported moderate headache following their high dose sessions.

Table 7.1-1: Adverse events reported during dosing sessions

Version Date: April 18, 2023

dose.

Adverse Event Description*	Low Dose (N = 52)	High Dose (N = 53)
Elevated Diastolic Blood Pressure (> 100)**	1 (2%)	7 (13%)
Elevated Systolic Blood Pressure (> 160)**	9 (17%)	18 (34%)
Elevated Systolic (> 160) and/or Diastolic Blood (> 100)	10 (19%)	18 (34%)
Elevated Heart Rate (> 110)**	1 (2%)	3 (6%)
Mild Headache	0	1 (2%)
Nausea/vomiting	0	8 (15%)
Paranoia	0	1 (2%)
Psychological Discomfort	6 (12%)	17 (32%)
Physical Discomfort	4 (8%)	11(21%)
Anxiety during session	8 (15%)	14 (20%)

^{*} AE during sessions refer to one or more instance(s) of the AE that occurred on session days after capsule administration; in all cases, the AE had resolved by the end of the

Spontaneously reported adverse events that occurred following psilocybin sessions that were judged to be possibly related to drug administration were rare, with four occurring following the low dose session and one occurring following the high dose session (Table 7.1-2). The reported adverse events judged to be possibly related to drug administration following lowerdose sessions included instances of a feeling of fullness in the chest (n=1), anxiety (n=1), insomnia (n=1) and decreased appetite (n=1). One instance of leg pain occurred following a

session day.

*** In one participant, the peak blood pressure magnitude (214/114 mmHg) met the protocol criterion for pharmacological treatment, however the protocol criterion for duration of elevation for pharmacological treatment was not met as the event lasted less than 15 minutes. In all cases blood pressure returned to normal levels by the end of the session.

Version Date: April 18, 2023 Con

higher-dose session. There were no cases of hallucinogen persisting perception disorder (HPPD) or prolonged psychosis.

Table 7.1-2: Adverse events reported after the psilocybin dosing session

Adverse Event Description*	Number of Instances	Causality
Death due to disease progression	2	Unrelated
Fullness in chest (post low-dose session)	1	Possible
Anxiety (post low-dose session)	1	Possible
Insomnia (post low-dose session)	1	Possible
Decreased appetite (post low-dose session)	1	Unrelated
Suicide after dropping out of study (did not receive high dose)	1	Unlikely
Eye infection (post low-dose session)	1	Unrelated
Coronary Artery blockage	1	Possible
Leg pain (post high-dose session)	1	Possible
Breast biopsy	1	Unrelated

^{*} AE not during sessions refer to any AE that occurred outside of sessions but after drug exposure during study participation until study termination, dropout, or completion of the six month follow-up; detailed event reports are appended

The New York University Study was a randomized, double-blind, placebo-controlled crossover study (NCT00957359) to investigate the efficacy of a single psilocybin dosing session versus placebo (in conjunction with psychotherapy) to treat clinically significant anxiety or depression in adults who received a cancer diagnosis. Participants were initially assigned to receive oral psilocybin (0.3mg/kg) or placebo (niacin, 250 mg), administered during an 8-hour treatment session. Crossover to the other arm occurred seven weeks after the first administration. Adverse events were monitored throughout the trial, including during and after dosing sessions. Primary outcomes of potential improvement of participant anxiety and depression were measured through 26 weeks after the second dosing session.

The most common adverse events that occurred during the psilocybin dosing sessions (before and after crossover, N = 28) included elevated systolic (>160 mm Hg) and diastolic BP (>100 mm Hg), headache and migraine, anxiety, and nausea. None of the elevated BP episodes required pharmacological intervention. One participant died as a result of cancer disease progression. Four subjects were withdrawn from the study due to disease progression and passed away shortly after withdrawal from the study. These serious adverse events were not attributed to psilocybin. Adverse events that occurred outside the dosing sections were collected, and causality from psilocybin was assessed (Table 7.1-3). Three of 11 events (27%) were determined to be possibly related to psilocybin administration.

Table 7.1-3: Adverse events not occurring during the psilocybin dosing sessions

Adverse Event Description*	Number of Instances	Causality
Community Acquired Pneumonia	1	Unrelated
Death due to disease progression	1	Unrelated
Hypotension	1	Unrelated
Lumbar Spinal Surgery	1	Unrelated
Migraine	1	Unrelated
Ocular Migraine	1	Unrelated
Experience of Thought Disorder	1	Possible
Neurosurgery	1	Unrelated
Visual Field Impairment	1	Possible
Vasovagal Syncopal Event	1	Possible
Vomiting	1	Unrelated

^{*} AE not during sessions refer to any AE that occurred outside of sessions but after drug exposure during study participation until study termination, dropout, or completion of the six month follow-up.

The University of California San Francisco study was single-arm, open-label, pilot study of psilocybin-assisted group therapy (NCT02950467). Participants were Gay-identified older longterm AIDS survivor (OLTAS) men \geq 50 years old, recruited from the community, who suffer from moderate-to-severede moralization (DemoralizationScale-II≥8). They receive 8-10 openlabel group therapy sessions over 8 weeks and one open label psilocybin individual session (0.3) mg/kg or 0.36 mg/kg po). Safety was evaluated with multiple measures. Every study visit included an adverse events assessment interview and the Columbia Suicidality Severity Rating Scale (C-SSRS) interval interview. Adverse events assessments during the medication visit included spontaneous participant self-report, events observed by clinicians, and symptoms derived from the Challenging Experiences Questionnaire⁵⁷ administered the next day. During psilocybin sessions, blood pressure and heart rate were assessed at regular intervals of 30 min for the first two hours, and then 60 min thereafter. At end-of-treatment, participant perceptions of benefits and harms from the intervention were assessed by a 7-point Likert scale (1= none at all; 7=extremely). The Schedule of Attitudes towards Hastened Death (SAHD) was administered at baseline, end-of-treatment and 3-month follow-up. The Montreal Cognitive Assessment (MoCA) was performed at enrollment and end-of-treatment. Because they were added after Cohort 1 completed the study, only Cohorts 2 and 3 completed the Alcohol Use Disorder Identification Test (AUDIT) and Drug Use Disorders Identification Test (DUDIT) at baseline and at the 3-month follow-up with a 'last 3 month' recall period.

Overall, zero serious adverse reactions and two unexpected adverse reactions to psilocybin were detected, and seven participants experienced self-limited, severe expected adverse reactions. Serious adverse events and adverse events are detailed in the following table.

Table 7.1-4: Adverse events during the UCSF study

Adverse events.

SAE Primary Term	# Participants (%), n = 18	Highest severity observed	Expectedness	Relatedness to Psilocybi
DURING INTERVENTION	" Turucipunto (10), 11	ingliest severnly observed	Expecteditess	neutralies to i shoeys.
Renal Cell Carcinoma	1 (5.6%)	Severe	Unexpected	Unrelated
Recurrence, Metastatic ^a	(23)			
Pneumothorax ^a	1 (5.6%)	Severe	Unexpected	Unrelated
DURING FOLLOW-UP	•		•	
Stimulant-induced psychosis ^b	1 (5.6%)	Potentially life-threatening	Unexpected	Unrelated
Suicide attempt ^b	1 (5.6%)	Potentially life-threatening	Unexpected	Unrelated
Cholecystitis	1 (5.6%)	Severe	Unexpected	Unrelated
Medication Visit Adverse Events (AE)			-	
AE Primary Term	# Participants (%), $n = 18$	Highest severity observed	Expectedness	Relatedness
Hypertension		Severe	Expected	Related
Severe (SBP≥180 or DBP≥110 mmHg)	4 (22.2%)		-	
Moderate (160 \(SBP < 180 \) or 100 \(DBP < 109 \)	8 (44-4%)			
Anxiety/Anxiety Exacerbation (moderate-severe)	8 (44.4%)	Severe	Expected	Related
Nausea	6 (33.3%)	Severe	Expected	Related
Headache	5 (27.8%)	Moderate	Expected	Related
Paranoia/Ideas of Reference	4 (22.2%)	Mild	Expected	Related
Motor Agitation / Restlessness	4 (22.2%)	Moderate	Expected	Related
Unsteady Gait / Ataxia	4 (22.2%)	Moderate	Expected	Related
Tachycardia	2 (11.1%)	Mild	Expected	Related
Thought Disorder	1 (5.6%)	Moderate	Expected	Related
Urinary Incontinence	1 (5.6%)	Moderate	Expected	Related
Visual Changes (complaint)	1 (5.6%)	Mild	Expected	Related
Post-Medication Visit Psilocybin-Related Adverse	Events		-	
AE Primary Term	# Participants	Highest severity	Expectedness	
Associated AEs	(%), n = 18	observed	-	
Headache	8 (44-4%)	Mild	Expected	
Fatigue	2 (11.1%)	Moderate	Expected	
Insomnia	2 (11.1%)	Mild	Expected	
Anxiety Exacerbation	1 (5.6%)	Severe	Expected	
Methamphetamine Relapse		Moderate	Unexpected	
Post-traumatic Stress Flashback	1 (5.6%)	Moderate	Unexpected	
Tinnitus, nausea, panic and insomnia			-	
Nausea	1 (5.6%)	Mild	Expected	

Adverse events were classified by the NIH DAIDS Table for Grading the Severity of Adult and Pediatric Adverse Events v2.0.

